Renal Transplant Injury and the Renin-Angiotensin System in Kids (RETASK) [name], PI

Abstract

Kidney disease is a major source of childhood morbidity and mortality. Kidney transplants improve quality of life and life expectancy. Renal graft injury is a significant problem and early identification is critical. No biomarkers exist to identify subclinical injury. Biopsies are the gold standard but are invasive and can miss early injury. The renin-angiotensin system (RAS) is activated in renal injury. The alternative RAS pathway ACE2/Ang-(1-7)/mas is important in counteracting these harmful effects. The components of these pathways are excreted in the urine and are altered in renal injury. The aims of this proposal are to develop noninvasive biomarkers of 1) early and 2) chronic subclinical graft injury. The project was an observational study with a convenience sample of children undergoing renal transplantation. The profile of these pathways in the urine will be compared to outcomes of 1) renal biopsy-confirmed early graft injury and 2) chronic graft injury using Cortical Fractional Interstitial Fibrosis Volume (V_{IntFib}) on biopsy specimens. The components of this pathway are novel potential biomarkers and have not been previously evaluated in this population. The findings of this proposal may enable more prompt diagnosis and more effective treatment of renal graft injury in children.

Specific Aims

In pediatric kidney transplant patients, rejection, medication toxicity and ischemia cause early and chronic renal allograft injury, which reduces graft lifespan and patient survival¹. Early identification of injury would facilitate prevention and treatment. The gold standard surveillance biopsy has limitations including delayed discovery of injury^{2,3}. No noninvasive test identifies graft injury before it is clinically apparent^{4,5,6}. This project's goal is to develop a novel early marker of subclinical graft injury to facilitate prompt recognition and treatment. Kidney damage activates the renin-angiotensin system (RAS), and the ACE2/Ang-(1-7)/mas pathway counteracts this damage.⁷ The balance, or ratio, between levels of RAS and the ACE2 pathway may be clinically important because the ACE2 pathway counteracts RAS-mediated injury. An increase in ACE and Ang II expression and a decrease in ACE2 and Ang-(1-7) expression on tubular cells may promote renal injury. Tubular damage may increase urinary loss of protective ACE2 and Ang-(1-7), propagating renal damage by allowing ACE and Ang II to stimulate inflammation and fibrosis unopposed.

Aim 1: Diagnose early subclinical graft injury in renal transplant patients with the ratios from ACE2 to ACE and from Ang-(1-7) to Ang II in urine. Hypothesis 1: A shift in the urinary ACE2 to ACE and Ang-(1-7) to Ang II ratios towards ACE2 and Ang-(1-7) predicts early subclinical graft injury diagnosed on renal biopsy. Aim 2: Diagnose chronic subclinical graft injury using the ratios of ACE2 to ACE and Ang-(1-7) to Ang II in the urine.

Hypothesis 2: A shift in the ACE2 to ACE and Ang-(1-7) to Ang II ratios in the urine towards ACE2 and Ang-(1-7) predicts chronic subclinical graft injury on renal biopsy.

Background/Significance

Angiotensin-converting enzyme (ACE) cleaves angiotensin (Ang) I into Ang II, which operates through the Ang II type 1 receptor (AT₁). The ACE2/Ang-(1-7)/mas pathway is an alternative, less characterized pathway that operates through the mas receptor⁸. ACE2 cleaves Ang II into Ang-(1-7) (figure 1). The exact mechanism of action of Ang-(1-7) is unknown but most data support its anti-inflammatory, anti-fibrotic and immune modulatory effects⁹⁻¹⁷. ACE2, Ang-(1-7) and mas expression is reciprocal to ACE, Ang II and AT₁ expression^{10, 12}. In the kidney, expression of ACE2 and Ang-(1-7) is greatest in the proximal tubules, especially the brush border membrane^{7,10,12,18,19}. The balance between the ACE and ACE2 pathways is critical in preventing renal fibrosis^{7,10,12}. Ang-(1-7) directly blocks Ang II and Ang II's downstream effects through the AT₁ receptor^{10,14,18-27}. ACE inhibitors (ACEi) and AT₁ blockers (ARB) reduce proteinuria and graft injury and improve graft function, independent of blood pressure^{32,37,38}. The ACE2 pathway may be responsible for these effects because it is enhanced at the expense of the RAS^{32,37-42}.

Tubulointerstitial damage decreases ACE2 expression, enhancing ACE and propagating injury^{43,44}. Urine ACE2 protein is elevated in renal transplant patients, independent of serum levels^{45,46}. These findings suggest that tubular damage causes shedding of ACE2 and Ang-(1-7) from the apical membrane of tubular epithelial cells into the tubular lumen and urine. Urinary excretion of ACE2 and Ang-(1-7) is altered in relation to ACE and Ang II. The ratios of ACE2/ACE and Ang-(1-7)/Ang II in urine could be noninvasive markers of subclinical graft injury. It is important to evaluate the balance between the ACE and ACE2 pathways because increased ACE2 could be due to increased expression of ACE2 or decreased ACE. ACE2/Ang-(1-7)/mas directly alters renal inflammation, making it an intriguing biomarker and therapeutic target.

Approach/Methods

This was an observational study with a convenience sample of patients recruited from Lucile Packard Children's Hospital's kidney transplant evaluation clinic from 2013 to 2015; 29 subjects completed the study. The recipient ages ranged 1 to 20 years and 34% were living donors. Stanford University School of Medicine IRB approval was obtained (IRB 5136) and informed consent and assent were obtained. Data was collected from information gathered per standard of care. Baseline and post-transplant data included age, sex, self-reported race (Black, White, Hispanic, Asian, or Other), presence of obesity (body mass index ≥95th percentile for age and sex), primary cause of end stage renal disease, dialysis modality, time on dialysis, presence of hypertension, use of ACEi/ARB, presence

of left ventricular hypertrophy, sensitization at transplant, creatinine, estimated glomerular filtration rate (eGFR) by modified Schwartz equation and urine creatinine and protein. Post-transplant data included deceased versus living donor transplant, antigen match, cold ischemia time, immunosuppression including drug levels, and protocol, and indication biopsy results. Specific to the study, plasma and urine protein ACE, ACE2, Ang II, and Ang-(1-7) were collected and analyzed. Data was collected at baseline and post-operatively at 12 hours, 24 hours, daily for 1 week, weekly for 1 month and monthly until 6 months post-transplant. Samples were collected at any clinically significant event concerning for graft injury, including a rise in creatinine, rejection, medication toxicity, and infection.

Subjects underwent a six-month surveillance protocol biopsy and some received three-month surveillance protocol or indication biopsies per standard of care. For the study, existing biopsy tissue was stained with Sirius Red, providing a measure of fibrosis called (V_{IntFib}) that was quantified by computerized image analysis⁴⁷. Fibrosis is an established measurement of chronic graft injury. ACE, ACE2, Ang II, and Ang-(1-7) protein were measured by radioimmunoassays at the Hypertension and Vascular Research Biomarker Analytic Core at Wake Forest School of Medicine. All data, including protected health information, was stored securely on a HIPAA-compliant REDCap Database hosted by Stanford University School of Medicine. Summary statistics, including frequencies for categorical variables and mean with standard deviation (SD) or median with interquartile range for continuous variables will describe clinical and demographic characteristics. Graphical exploration will assess the data and quantile plots will evaluate the need for log transformation. Measurements below the lower limit of detection of the laboratory will be assigned a value of the lower limit of detection divided by the square root of two. Spearman rank correlation coefficients will be used to assess the correlation between ACE2, ACE, Ang-(1-7), Ang II and the continuous covariates and outcomes. We will estimate sensitivity, specificity, and the area under the receiver operator characteristics curve to assess the clinical predictive value of the biomarkers.

Primary outcome for Aim 1: Early subclinical graft injury.

Cox regression will be used to estimate hazard ratios for the association of biomarker levels with the outcome biopsy-proven graft injury, adjusting for potential confounders. Robust standard errors and clustering by subject ID for patients diagnosed with more than one episode of graft injury during the study period will be used. The time axis will be six months, starting at the time of transplant or time of recovery from the preceding acute injury event, and ending at six months post-transplant. Observations will be right-censored at the time of graft loss, loss to follow up, or withdrawal from the study. The model will be compared to other models that include the time dependent-covariates serum creatinine and eGFR.

Primary outcome for Aim 2: Chronic subclinical graft injury.

Cox regression will be utilized to estimate hazard ratios for the association of biomarker levels with the outcome biopsy-proven graft fibrosis, adjusting for potential confounders. The time axis will begin at the time of transplant and end at six months post-transplant. Observations will be right-censored at the time of graft loss, loss to follow up, or withdrawal from the study. The model will be compared to other models that include the time dependent-covariates serum creatinine and eGFR.

Missing Data

Subjects may miss lab collections or may be lost to follow up. However the reasons for missing data are presumed to be independent of the values of the predictors ACE, ACE2, Ang II, and Ang-(1-7). Clinical data including covariates and outcomes will be recorded even if a subject is lost to follow up. Therefore missing data will be presumed to be missing completely at random. We chose to handle missing covariate values by multiple imputations due to the longitudinal data and high rate of missing data (23%).

Power

The study was estimated to enroll 30 subjects (final enrollment 29), based on anticipated subjects and estimated incidence of kidney injury (10% in first six months post-transplant). The study was powered to detect a Pearson correlation of 0.56 with a two-sided *p* value of 0.025.

References

- 4. Halawa A. The early diagnosis of acute renal graft dysfunction: A challenge we face. The role of novel biomarkers. Ann Transplant. 2011; **16**(1): 90-8.

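### ACEi/ARB use may move the urinary marker in the direction read as injury, and the planned Spearman and ROC analyses do not account for it although use is recorded

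*Combined protocol and SAP*

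**What the plan says.** **Direction read as injury.** Specific Aims, Hypothesis 1: "A shift in the urinary ACE2 to ACE and Ang-(1-7) to Ang II ratios towards ACE2 and Ang-(1-7) predicts early subclinical graft injury". Hypothesis 2 uses the same direction for chronic injury.

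**Effect of the drugs.** Background/Significance says that ACE inhibitors and AT₁ blockers "reduce proteinuria and graft injury and improve graft function, independent of blood pressure", and continues: "The ACE2 pathway may be responsible for these effects because it is enhanced at the expense of the RAS". The hedge applies to whether the pathway explains the benefit; the enhancement itself is given as the reason. The same section warns that "increased ACE2 could be due to increased expression of ACE2 or decreased ACE", so it accepts that ACE2 can rise for reasons other than tubular shedding.

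**What is recorded.** Approach/Methods lists "use of ACEi/ARB" among the baseline and post-transplant data. It gives no number of users and no start or stop dates, and states no exclusion for use.

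**What is analysed.** Approach/Methods plans Spearman correlations of the four analytes with continuous covariates and outcomes, and then: "We will estimate sensitivity, specificity, and the area under the receiver operator characteristics curve to assess the clinical predictive value of the biomarkers". Neither analysis is described as restricted, stratified or adjusted. The Cox models under Aims 1 and 2 adjust for potential confounders, which are not named.

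**The concern.** These drugs act on the axis being measured. On the document's own account they enhance the ACE2 side while lowering injury. If that enhancement shows in urine, a treated child with a healthy graft can have a ratio that the hypotheses would call injury. Drug use would then be related to both marker and outcome, which is confounding for an unadjusted correlation. A cut-off that performs well off drug would also give more false positives on drug.

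At stake is how the accuracy results are read. A weak AUC might partly reflect drug use. A good one might too, if treated children happened to be the injured ones. The reader could not tell, because nothing is planned by drug use outside the Cox models.

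**Working it through.** **The plan's own figures.** The plan gives no figure for drug use or drug effect. Its power statement (Pearson correlation 0.56, two-sided 0.025) does not state the power. By Fisher's z, n = ((2.241 + 1.036)/0.6328)² + 3 = 29.8, so 30 subjects fits 85% power. The present point does not depend on this. The figures that matter are 29 subjects and 10% incidence: 0.10 × 29 = 2.9, about 3 injured children.

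**Assumed inputs (none from the documents).** The log ratio is normal with SD 1. Injury raises it by 1 SD. The drug raises it by g = 0.5 to 1.5 SD. q0 and q1 are the proportions on drug among uninjured and injured children.

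**AUC within a drug stratum.** Φ(1/√2) = 0.760.

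**Pooled AUC.** A random injured–uninjured pair either has the same drug status, or only one member is on drug:

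AUC = [q1·q0 + (1−q1)(1−q0)]·Φ(1/√2) + q1(1−q0)·Φ((1+g)/√2) + (1−q1)q0·Φ((1−g)/√2)

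With 30% use in uninjured and 10% in injured children the weights are 0.66, 0.07 and 0.27:
- g = 0.5: 0.66 × 0.760 + 0.07 × 0.856 + 0.27 × 0.638 = 0.73
- g = 1.5: 0.66 × 0.760 + 0.07 × 0.962 + 0.27 × 0.362 = 0.67

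Reversing the rates swaps the last two weights:
- g = 0.5: 0.66 × 0.760 + 0.27 × 0.856 + 0.07 × 0.638 = 0.78
- g = 1.5: 0.66 × 0.760 + 0.27 × 0.962 + 0.07 × 0.362 = 0.79

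| Use, uninjured v injured | g = 0.5 | g = 1.0 | g = 1.5 |
|---|---|---|---|
| 30% v 10% | 0.73 | 0.70 | 0.67 |
| 30% v 30% | 0.75 | 0.74 | 0.72 |
| 10% v 5% | 0.75 | 0.74 | 0.73 |
| 10% v 30% | 0.78 | 0.79 | 0.79 |

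With no drug shift, every row is 0.76. With g = −0.5 and use of 30% v 10%, the AUC is 0.78.

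**False positives in treated, uninjured children.** For a cut-off giving 10% off drug, the on-drug rate is 1 − Φ(1.28 − g): 22% at g = 0.5, 39% at 1.0 and 59% at 1.5. This does not depend on use rates; it needs only g > 0.

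**Precision.** The Hanley–McNeil standard error at AUC 0.76 with 3 injured and 26 uninjured children uses Q₁ = 0.76/(2 − 0.76) = 0.613 and Q₂ = 2 × 0.76²/(1 + 0.76) = 0.656:

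SE = √{[0.76 × 0.24 + 2 × (0.613 − 0.578) + 25 × (0.656 − 0.578)]/(3 × 26)} = 0.169

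The 95% half-width is 1.96 × 0.169 = 0.33. This is wider than any AUC shift in the table, even before samples are excluded.

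**The case against.** **Urine is not tissue.** The documents describe the pathway under these drugs, not urinary ratios. Their shedding mechanism lets the two differ: damage lowers tissue ACE2 while increasing urinary loss. Less injury on drug could even mean a lower urinary ratio. This stands, so the concern must remain conditional.

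**The size is unknown.** The documents give no use rates, and a zero or negative drug shift is possible. This stands. A reader might infer that the AUC must be pulled towards 0.5; the table shows that it can move either way.

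**The aims have adjusted analyses.** A reader might infer that the trial could not answer Aims 1 and 2. The documents do not support that. Under each aim's primary outcome the stated analysis is a Cox model adjusting for potential confounders, and ACEi/ARB use is recorded and could be among them.

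**Pooling can be the right target.** If the test is meant for all transplanted children, pooled accuracy is a legitimate quantity, and false positives on drug are a real limitation of the marker. This stands, and with about 3 injuries an off-drug primary ROC would be a poor trade. It does not remove the value of showing results by drug use.

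**Spearman names analytes, not ratios.** This is true, but a drug that raises ACE2 or Ang-(1-7) in urine would confound those correlations as well.

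**Conclusion.** The point holds in conditional form and is a low-cost improvement, not a defect that undermines the study. By the document's account, ACEi/ARB lower injury and enhance the pathway whose urinary rise is read as injury. The Spearman and ROC analyses ignore a variable that is already recorded. That these analyses pool on-drug and off-drug samples is inferred from the absence of any other rule.

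If the drug raises the urinary ratio, false positives rise among treated, uninjured children: from 10% to between 22% and 59% under assumed shifts of +0.5 to +1.5 SD. The effect on the pooled AUC has no fixed sign: 0.73 to 0.67 with 30% v 10% use, and 0.78 to 0.79 with the reverse, against 0.76 off drug. All of these rest on assumed shifts and use rates. What is affected is the interpretation of the accuracy and correlation results; the adjusted Cox models remain.

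**What to change.** Keep the pooled ROC as planned. Add to the statistical methods in Approach/Methods:

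- Spearman correlations are also reported as partial correlations adjusted for ACEi/ARB use at the time of sampling.
- Marker levels and false-positive rates (1 − specificity) in uninjured samples are shown separately on and off ACEi/ARB.
- The ROC analysis is repeated without on-drug samples as a sensitivity analysis, where estimable.
- Current ACEi/ARB use is included among the Cox confounders if the number of events allows.

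This needs no new patients or assays. The cost is a little more analysis and the work of matching recorded drug use to sample dates; the plan does not say whether use was recorded with dates. With about 3 expected injuries, the subgroup ROC will be imprecise and may not be estimable. The comparison in uninjured samples does not depend on the number of injuries, and it addresses directly whether the marker differs with drug use.

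### Aim 1 neither lags nor excludes samples triggered by suspected injury, so its hazard ratio and AUC can reflect concurrent, clinically apparent injury instead of prediction of subclinical injury

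*Combined protocol and SAP*

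**What the plan says.** All references are to the combined protocol and SAP.

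- **Sampling (Approach/Methods).** After baseline, 12 hours and 24 hours, samples follow a fixed schedule: "daily for 1 week, weekly for 1 month and monthly until 6 months post-transplant". A second stream depends on clinical events: "Samples were collected at any clinically significant event concerning for graft injury, including a rise in creatinine, rejection, medication toxicity, and infection".
- **How injury is found (Approach/Methods).** "Subjects underwent a six-month surveillance protocol biopsy and some received three-month surveillance protocol or indication biopsies per standard of care".
- **Aim 1 analysis (Primary outcome for Aim 1).** "Cox regression will be used to estimate hazard ratios for the association of biomarker levels with the outcome biopsy-proven graft injury". The exposure is not defined as a baseline, latest, average or time-updated value. There is no lag and no rule for triggered samples. Injury from indication biopsies and injury from protocol biopsies count alike. Sensitivity, specificity and ROC area are also planned, again with no rule on which sample is used.
- **Comparators (same paragraph).** "The model will be compared to other models that include the time dependent-covariates serum creatinine and eGFR". These are the only variables to which the plan gives a time-dependent form.
- **The claim to be supported (Specific Aims).** Hypothesis 1 is that a shift in the urinary ratios "predicts early subclinical graft injury diagnosed on renal biopsy". The motivation is that "No noninvasive test identifies graft injury before it is clinically apparent".

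**The concern.** A sample drawn because creatinine has risen or rejection has occurred is drawn when the injury is already visible. If that value is the exposure for the same injury, the model measures how the marker behaves during overt injury and says nothing about whether it moved beforehand.

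The plan's own biology makes this a live issue. Specific Aims and Background both expect tubular damage to shed ACE2 and Ang-(1-7) into the urine, so an event-day value may be a result of the injury. Infection or drug toxicity might also move the marker.

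At stake is how Aim 1 is read. An HR or AUC built partly on triggered samples could be reported as evidence of early, subclinical detection when it shows agreement with a clinical picture already apparent. The comparison with creatinine and eGFR is also hard to interpret while the biomarkers have no timing rule.

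**Working it through.** **Inputs from the documents.** 29 subjects and 10% injury incidence in six months (Power); the sampling schedule and triggers (Approach/Methods).

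**Assumed, because the documents give no figure.** Marker SD of 1; a shift of 0, 0.5 or 1 SD that appears on the event day and not before (no advance information, unless stated); stationary within-subject noise; last value carried forward between samples.

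**Step 1. The plan's own figure.** Using Fisher's z for r = 0.56 and two-sided 0.025, n = ((z_alpha + z_power)/atanh(r))² + 3. At an assumed 85% power, n = ((2.241 + 1.036)/0.633)² + 3 = 29.8. At 80% it is 26.7, and at 90% it is 34.0. The planned 30 is consistent with 85% power, but no power is stated. This calculation concerns a correlation and does not bear on sample timing.

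**Step 2. Events.** 0.10 × 29 = 2.9 expected. The chance of none is 0.9^29 = 0.047.

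**Step 3. Closed form.** If the marker is normal with SD 1, and cases are shifted by δ when sampled, the ratio of case to at-risk density at x is exp(δx − δ²/2). The HR per SD is therefore exp(δ), and AUC = Φ(δ/√2).

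- δ = 0: HR 1.00, AUC 0.50
- δ = 0.5: HR 1.65, AUC 0.64
- δ = 1: HR 2.72, AUC 0.76

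**Step 4. Simulation on the plan's schedule.** Cox partial likelihood, 10% events, 40 runs of 500 subjects each, so that bias shows apart from small-sample noise. Monte Carlo standard error of the log HR is 0.02 to 0.03. Entries are HR per SD.

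| Setting | Event-day triggered sample used | Only samples before the event day |
|---|---|---|
| No shift | 0.99 | 1.04 |
| 0.5 SD, all cases triggered | 1.70 | 1.02 |
| 1 SD, all cases triggered | 2.61 | 0.98 |
| 1 SD, half of cases triggered | 1.57 | 1.00 |
| 1 SD, no case triggered | 0.98 | 1.02 |
| 1 SD, shift begins 14 days early | 2.68 | 1.73 |

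**Step 5. What drives it?** A second set (100 runs of 500, 1 SD shift) compared three rules.

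- Case sampled on the day, others carried forward: 2.82
- Everyone sampled on the day: 2.71
- Everyone's last scheduled value before the day: 1.00

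The driver is therefore concurrency with the injury; having a fresh value only in the case adds little. With no shift but a time trend of +2 or −2 SD over six months, freshness in the case alone gave 1.17 or 0.87, so that component can act in either direction. With a shift starting 14 days early, the first and third rules gave 2.78 and 1.74.

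**Step 6. At the study's size.** With 29 subjects and a 1 SD shift (381 of 400 runs had an event), the median HR was 2.67 (interquartile range 1.70 to 5.12) with triggered samples and 0.94 (0.67 to 1.51) with earlier samples only.

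**Step 7. Where the exposure lies.** Scheduled samples are daily in week 1 and weekly in month 1, so early triggered samples differ little in timing from scheduled ones. Injuries found at three- or six-month protocol biopsies fall near the monthly samples. What remains is indication-biopsy injury, mainly after month 1, when scheduled samples are about 30 days apart. The documents do not give the number of such cases.

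**The case against.** The strongest reply is that the plan never says triggered samples enter the model. If the exposure were a baseline value, none would. That is right, and it limits the point to what can happen under the text as written. It does not remove the point: these are listed as study samples, nothing excludes them, and the choice can move the HR of an uninformative marker from about 1.0 to well above it.

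A second reply is that Aim 1 is worded as diagnosis, so a marker that moves while injury is present is the intended signal. This stands for a scheduled sample taken at a protocol biopsy, where the injury may be silent, and the repair keeps those samples. It does not rescue samples prompted by clinical signs, because Hypothesis 1 speaks of prediction and the target is subclinical injury.

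Third, if the biomarkers are time-updated, creatinine is available at the event too, so the model comparison need not be unequal. That also stands: the defect there is an unstated rule, and a mismatch is not shown.

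Two stronger readings are tempting. A reader might infer that the Aim 1 HR is inflated. The documents do not support this: it needs triggered values in the model and a marker that moves with illness or injury, and neither is established. A reader might also infer that cases have an event-day value that other subjects lack. But infection and medication toxicity are triggers too and can occur without biopsy-proven injury, early sampling is dense for everyone, and Step 5 shows that case-only freshness is not the main cause.

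**Conclusion.** The concern holds in a conditional form. Aim 1 leaves open the use of values drawn at clinical suspicion, and to that extent its HR and AUC cannot support Hypothesis 1. It should be corrected because the gap affects what the result means, and closing it needs no new data.

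The size rests on an assumed event-day shift with no source in the documents. At 0.5 to 1 SD, with every case triggered, an uninformative marker shows an HR of about 1.7 to 2.7 per SD. That is an upper scenario, since cases found by protocol biopsy need not be triggered. With half triggered and a 1 SD shift it is about 1.6; with no shift, or with earlier samples only, about 1.0. These figures show direction and range and are not an estimate for this study. With about 3 expected events, any Aim 1 HR will be very imprecise whichever rule is used.

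**What to change.** In the paragraph on the primary outcome for Aim 1:

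1. Define the primary exposure as the time-updated urinary ACE2/ACE and Ang-(1-7)/Ang II ratios from the latest scheduled post-transplant sample. For a protocol biopsy, this is the latest such sample on or before the biopsy. For an indication biopsy, it is the latest one before the trigger date.
2. Use the same timing rule for serum creatinine and eGFR in the comparison models.
3. Apply the rule to the ROC, sensitivity and specificity analyses as well as to the Cox model.
4. Report triggered samples separately, labelled as the marker at clinical suspicion.
5. Report protocol-biopsy (subclinical) injury apart from indication-biopsy injury, with the number of each.

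The cost is a few sentences of SAP text and a scheduled-or-triggered label on each sample. The statistical price is that the exposure for indication cases can be up to about a month old, so some real short-lead signal is lost. If the marker truly shifts 14 days early, the HR would be about 1.7 where event-day samples would give about 2.7. The separate analysis in item 4 retains that information.

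### Aim 1 fits an ordinary Cox model with an unstated number of confounders on about 3 expected events, so with two or more confounders the hazard ratio is often too far from 1 or not finite

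*Combined protocol and SAP*

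**What the plan says.** Under the Aim 1 primary outcome in Approach/Methods, Cox regression relates biomarker levels to the outcome, "with the outcome biopsy-proven graft injury, adjusting for potential confounders". The plural is the only indication of how many confounders there are. Approach/Methods lists well over a dozen baseline and post-transplant variables as collected data, but does not call them the adjustment set.

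The next steps are a comparison, "The model will be compared to other models that include the time dependent-covariates serum creatinine and eGFR", and a variance provision: "Robust standard errors and clustering by subject ID for patients diagnosed with more than one episode of graft injury". The time axis runs "starting at the time of transplant or time of recovery from the preceding acute injury event, and ending at six months post-transplant".

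The Power section gives the sample size, "The study was estimated to enroll 30 subjects (final enrollment 29", and bases it partly on the "estimated incidence of kidney injury (10% in first six months post-transplant". Its only power statement concerns something else: "The study was powered to detect a Pearson correlation of 0.56 with a two-sided" p value of 0.025. Approach/Methods confirms that "29 subjects completed the study".

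The plan gives no event-based calculation for the Cox model, no limit on covariates, no minimum event count, and no penalised or exact method.

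**The concern.** A Cox model draws its information from events, not from subjects. When the covariates approach the events in number, the partial likelihood may have no finite maximum, and the estimates that are finite tend to lie too far from 1. With about 3 events, two or three confounders are enough to reach that point.

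The adjusted hazard ratio is the named regression result for Aim 1. A large value produced by overfitting could be read as support for a urinary marker of graft injury in children, and the comparison with the creatinine and eGFR models could inherit the same instability. An open confounder list also lets the adjustment set be chosen after the estimates are seen.

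**Working it through.** **1. The plan's own sample-size figure.** The Power section gives r = 0.56 at two-sided 0.025, with no power level. By Fisher's z, N = ((z for 0.0125 + z for power) / atanh(0.56))² + 3. At 85% power, ((2.241 + 1.036) / 0.633)² + 3 = 29.83, so 30. At 80% power the result is 26.73, so 27. The planned 30 fits 85% power, or 80% power with an assumed 10% loss (27 / 0.9 = 30). Neither says anything about the Cox model.

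**2. Expected events.** 30 × 0.10 = 3.0 as planned and 29 × 0.10 = 2.9 as enrolled. Under Binomial(29, 0.10), P(0) = 4.7%, P(3 or fewer) = 67% and P(5 or more) = 16%.

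**3. Information before any adjustment.** With 3 events, SE(log HR per SD) is about 1/√3 = 0.58. The 95% interval is then the hazard ratio divided and multiplied by exp(1.96 × 0.58), about 3.1.

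**4. One binary confounder, by counting.** Approach/Methods reports 34% living donors, about 10 of 29. If 3 events fall at random, the chance that all share one donor type is [C(10,3) + C(19,3)] / C(29,3) = (120 + 969) / 3654 = 30%. The donor-type coefficient is then infinite.

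**5. Simulated size of the problem.** Assumptions not in the documents: 29 subjects, exactly 3 events, independent continuous covariates, true HR 2 per SD, ordinary partial likelihood.

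| Confounders added to the biomarker | Median HR | HR above 20 or below 1/20 |
|---|---|---|
| 0 or 1 | 2.0 to 2.2 | about 2 to 4% |
| 2 | about 2.5 | about 11% |
| 3 | about 2.7 | about 17% |
| 5 | not stable | about 43% |

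Separate runs differ by a few percentage points. A Firth-penalised fit with the same two or three confounders gives a median of 1.9, with 2 to 3% extreme. The gain therefore comes from the penalty as well as from dropping covariates.

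**6. No finite maximum, 3 events, true HR 1 or 2.** With some confounders binary (prevalence 34% and 50%), 35 to 36% of fits with two confounders and 49 to 55% with three have no finite maximum. With three continuous confounders it is 5 to 11%. The infinite coefficient often belongs to a confounder. With three confounders, the biomarker's own hazard ratio is above 10 or below 0.1 (a looser cut-off than in step 5) in 8 to 11% of fits at true HR 1 and 19 to 23% at true HR 2.

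**7. Sensitivity to the event count.** With three continuous confounders and true HR 2, the extreme share by the 20-fold rule falls from about 17% at 3 events to about 3 to 5% at 6 and under 1% at 9. With three confounders of which two are binary, and events drawn at random, no finite maximum occurs in 53 to 55% of fits at a 10% rate, 21 to 22% at 20% and 5 to 6% at 30%.

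**8. The plan's other provisions.** Clustered robust standard errors concern the variance and cannot make an infinite estimate finite. The Missing Data section specifies multiple imputation of covariates, which averages coefficients over several fits, so one divergent fit can spoil the pooled value.

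**The case against.** The strongest reply is that the size depends on two numbers the documents do not give: how many confounders are used and how many events occurred. With one confounder the ordinary fit is acceptable. The 10% is a planning rate for kidney injury, repeat episodes count, and the endpoint includes subclinical injury found on surveillance biopsy, so the count may exceed 3. Both points stand, and the result should be read as a range.

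The simulations also omit recurrent episodes, time-dependent covariates, missing data and ties at the six-month biopsy. That stands too: the percentages illustrate the mechanism and do not estimate this study's error. Aim 1 evidence will also come from Spearman correlations and from sensitivity, specificity and ROC area, so the hazard ratio does not stand alone. This lowers the severity.

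A reader might infer more than the text supports:

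- *That creatinine and eGFR are stacked on the full confounder set.* The plan puts them in other models used for comparison and does not say what else those models contain. If both were added to three confounders at 3 events, 61 to 67% of fits would have no finite maximum, but that is conditional on a reading the text does not settle.
- *That the hazard ratio will be too large.* Under no effect the errors run about equally in both directions; too far from 1 is the accurate description.
- *That the false-positive rate is known to be inflated.* An inflated rate can be shown for a likelihood-ratio test with five confounders, but the plan names neither that test nor that number.

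**Conclusion.** The concern holds as a conditional one. The planning figures imply about 3 events, and the stated method, an unpenalised Cox model with an open list of confounders, becomes unreliable once two or more are included. At two or three confounders and a true HR of 2, the median is pushed to about 2.5 to 2.7 and about 11 to 17% of fits are beyond 20-fold; binary confounders make non-finite fits common. At none or one confounder, or at 6 events or more with few continuous confounders, the problem is small.

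This is more than missing detail, because an available method does better with the same covariates. The comparison models meet the same limit if creatinine and eGFR are added to the confounders. The conclusion rests on the 10% rate, on one event per child in the simulations, and on assumed covariate distributions. Severity: should be fixed.

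**What to change.** In the Aim 1 section:

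- Fit the Cox models by Firth-penalised partial likelihood, and state how this is combined with the clustering by subject already specified.
- Replace the open reference to confounders with a very short set named before the analysis and sized to the observed event count, for example one covariate at about 3 events.
- Enter serum creatinine and eGFR in separate comparison models, because eGFR is computed from creatinine, and say which other covariates those models carry.
- Report the number of events and of children with an event, and label the adjusted hazard ratio exploratory when events are few.

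The cost is a change of wording and a penalised-likelihood routine; no new data are needed. The estimate is shrunk slightly (median about 1.9 against a true 2 in the simulations), and there is less control of confounding in the regression, though about 3 events could not support that control in any case. The exact size of the adjustment set is a judgement. What matters is that it is fixed in advance and tied to the event count.
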